***Withdrawal Procedures:***

Volunteers will be withdrawn if the research team, clinician and/or safety officer feels that further participation in the study or performance of any procedure associated with this study would, in any way, put the volunteer at undue risk or not be in their best interest. Moreover, volunteers may be withdrawn if s/he fails to attend scheduled visits or do not comply with instructions from research staff.

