**Study Design:**

Patients with recent, unilateral ACL rupture or combined ACL rupture/meniscus injury, who are undergoing surgical reconstruction, will be recruited and randomized to active NMES or control (placebo) interventions, with stratification for age, sex and graft type (knee extensor autograft, knee flexor autograft or allograft). All personnel performing assessments on patients/tissue will be blinded to group assignment. A within-subject design will be used, where the injured, surgically-treated leg will be compared to the contralateral, uninjured leg. NMES or control interventions will begin shortly following injury (within 3 wks) and run till 3 wks post-surgery. Patients will be evaluated twice pre-surgery and then at 3 wks and 6 mos post-surgery. There is the possibility for an additional visit prior to Pre-Surgery Testing #1 to assure that we consent volunteers and start the NMES/control intervention prior to 3 week post-injury. We will make every attempt to limit this

**Pre-surgery testing #1** (within 3 wks of injury) will consist of clinical/patient-oriented assessments (IKDC, KOOS) and functional testing (uninjured leg only).

**Consent/Device Training Visit** will occur within 3 wks of injury to begin the NMES/control intervention if the Pre-surgery testing #1 visit cannot be scheduled within this time constraint. Volunteers will be consented and will undergo training in the use of the NMES or control intervention (detailed below).

**NMES/Control intervention** will begin within 3 wks of injury following pre-surgery testing, with patients randomized (1:1). Active NMES intervention will consist of active NMES 5 d per week, with each session lasting 60 min. For the control intervention, volunteers will receive a sham NMES device to maintain blinding and will be told that they will receive imperceptible, microcurrent stimulation for pain mitigation. In the sham device, electrical leads are disconnected so that no current can leave the NMES device.

**Pre-surgery testing #2** (~1 wk pre-surgery) will be identical to Pre-surgery #1 testing, but will include strength testing of the injured leg.

Post-surgery testing #1 (3 wks) will consist of bilateral muscle biopsies for cellular structure and function measures and bilateral thigh muscle size assessments.

Standardized rehabilitation will begin 3 wks post-surgery, with both groups undergoing the same accelerated rehabilitation program that is standard of care within our practice.

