An issue with the built-in compliance monitoring feature is that the research team only learns of volunteer non-compliance after s/he returns that device. That is, if the volunteer is not truthfully completing the self-reported compliance log and reporting non-compliance during weekly phone contacts, s/he could be skipping NMES sessions without the research team's knowledge. To overcome this problem and to improve compliance with the NMES intervention, we have designed a modified NMES device and smartphone/tablet app that allows for real-time monitoring of compliance with the NMES prescription. In collaboration with [name], an assistant professor in the Dept. of Computer Science, as well as a senior engineering capstone design group, we have designed a cyber-physical system that provides real-time compliance tracking of NMES use. This is detailed in the attached proposal, which was funded by a LCOM/CEMS Biomedical Engineering Pilot Grant. Briefly, this system encompasses three components: an instrumented NMES device, a smartphone app and a back-end server program with automated compliance analysis capabilities. The instrumented NMES contains a low-cost, low-powered, embedded device that detects, quantifies and stores NMES device use data and can transmit these data via Bluetooth (detailed in attached Appendix to Amendment 11). The smartphone app is able to acquire data (data pull) from the instrumented NMES device and communicate the data to a back-end server via the Internet, where data will be stored, analyzed, and made available to care providers. Finally, there is software on a HIPAA compliant portion of the LCOM server that will store these data and analyze them to calculate compliance with the NMES regimen. We will ask volunteers to use this device to test the utility of this cyber-physical system to track compliance with the NMES prescription. The device itself does not work any differently than a standard NMES device, with the exception of the requirement to turn on an additional power switch. The smartphone/tablet app is simple to use and the volunteers will be instructed on its use. Finally, the server-based software is also designed to automatically send 'push' notifications to the volunteer's phone/tablet to provide positive reinforcement when s/he completes assigned NMES sessions and to inquire if there are any problems or if the volunteer would like to contact the research team if there is non-compliance. In addition to these contacts, the research coordinator will be in contact with the volunteer on the usual schedule of interactions (once per week) to inquire about compliance and any issues the volunteer might be having with the NMES device. Finally, the app is written for the iOS operating system. If the volunteer does not have a compatible device, we will loan them a device for the duration of the study.

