**Number of Subjects:**

We intend to enroll a total of 24 volunteers. This will allow for n=20 to complete the study, conservatively assuming 20% total attrition rate.

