To obtain data to estimate samples sizes based on these relative differences, we used a larger data set of knee OA patients (n=16) assessed for identical measurements proposed in this application (single fiber CSA and function). Mixed linear models were developed to estimate both between cluster variances and intraclass correlation coefficients (ICC), where samples were obtained at times before and after treatment, with clusters of fibers available for each volunteer at each time point. Cluster variance and ICC estimates were 1,030,622 and 0.337 for MHC I CSA; 1,047,066 and 0.383 for MHC II CSA; 254 and 0.263 for MHC IIA tension and 576 and 0.610 for MHC IIA velocity, respectively. These data were then used in a two group repeated measures analysis of variance model to estimate power for group, leg and group X leg interaction effects. Using relative differences detailed above and variance estimates from our mixed model analyses, we estimated that an n=10/group would detect significant group X leg interaction effects for MHC I CSA and MHC IIA tension and velocity, with powers in excess of 80% (87%, 99% and 99%, respectively) at a significance level of 5%. We chose these three variables because they represent important determinants of whole muscle size and function. More specifically, as the most prevalent fiber type in muscles (3, 4), MHC I CSA is the most important factor determining whole muscle size. Similarly, given that MHC IIA fibers are the most prevalent fast-twitch, type II fiber in human muscle, it disproportionately determines the contractile characteristics of whole muscle because of its large power output (2, 5). Power output is dependent on both the force producing capacity and contractile velocity of the constituent fibers (ie, power=force X velocity). Thus, we have included both force and velocity in our sample size estimates. Of note, we did not focus on MHC IIAX fiber function because, unlike our studies in older adults, where these fiber types are much more prevalent, far fewer of these fibers are present in younger adults (4), who will comprise the majority of our ACL injured population. Assuming ~20% dropout rate, based on our prior work (6-8), we will enroll 12 individuals/group with the expectations of a final sample size of 10/group.

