In Aim 2, our primary outcome is knee extensor isokinetic torque. Using our data in ACL reconstructed patients (Fig 1), we anticipate reductions in isokinetic muscle strength at 6 months post-surgery of -30% vs. uninjured leg in volunteers randomized to the control group (10). Given the effect of NMES to prevent atrophy and contractile dysfunction at the cellular level (Fig 2) and preliminary evidence from others showing that NMES maintains whole muscle size and strength post-surgery (11), we predict that loss of isokinetic strength will be minimal at 6 months (~5% loss or 95% of uninjured) in the NMES group. Based on these differences, a sample of n=10/group would detect a group X leg interaction effect with 80% power and a significance level of 0.05. We have not performed sample size estimates on secondary outcome variables, as it is unlikely that our sample size and length of follow-up will be sufficient to detect effects of NMES on these factors. In anticipation of observing salutary effects of NMES on muscle size and function (Aim 1), analyses of these secondary outcome variables will provide preliminary data to inform power calculations for future randomized controlled clinical trials to interrogate broader clinical efficacy of NMES to mitigate skeletal muscle structural and

functional adaptations to traumatic knee injury and surgical intervention, with the goal of mitigating long-term knee pathology (10).

Statistical analytical approach: Our primary goal is to assess the effect of group assignment (NMES vs. control) on skeletal muscle fiber size and contractile function 3 wks post-surgery using a mixed model, with group and leg (injured vs. non-injured) as fixed effects and subject ID and fiber number as random effects to account for the pairing of legs and clustering of fibers within each volunteer, respectively, as generally described (21). Primary outcomes include: MHC I and II fiber CSA and MHC IIA tension (force/CSA) and velocity. Any confounding factors differing between groups (eg, physical activity level, time between injury and surgery, tourniquet time during surgery) can be included as covariates, although most factors should be balanced by randomization.

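### The rule allowing withdrawal for missed visits or non-compliance can bias the arm comparison, because it does not separate stopping the device from leaving follow-up and the SAP states no as-randomised analysis

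*Protocol*

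**What the plan says.** Protocol, Withdrawal Procedures, gives two grounds for removal. The first is safety or the volunteer's best interest, and it is not at issue here. The second is that "volunteers may be withdrawn if s/he fails to attend scheduled visits or do not comply with instructions from research staff". It carries no threshold, names no decision-maker, and does not say whether outcomes are still collected afterwards.

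Protocol, Procedures (Primary Aim), takes fiber size and contractile function from bilateral biopsies at one time point, 3 weeks after surgery. Knee extensor torque, the Aim 2 primary outcome, is compared at 6 months.

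Protocol, Interventions, describes an instrumented NMES device whose use data go to a server that will "analyze them to calculate compliance with the NMES regimen". The described response to non-compliance is app messages and a weekly contact by the research coordinator. Data Safety and Monitoring states that this coordinator is not blinded.

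On numbers, the protocol says "We intend to enroll a total of 24 volunteers" and "This will allow for n=20 to complete the study, conservatively assuming 20% total attrition rate". The SAP says "we will enroll 12 individuals/group with the expectations of a final sample size of 10/group". Its Statistical analytical approach specifies mixed models with group and leg effects. It names no analysis set, no as-randomised principle, no missing-data method and no sensitivity analysis.

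**The concern.** Withdrawal for missed visits or non-compliance happens after randomisation. With a single primary assessment, leaving the study before the biopsy means having no primary outcome. The within-subject design does not protect against this. The uninjured leg controls for differences between people, but the group-by-leg effect still compares one set of people with another, and that comparison is protected only while the randomised groups stay intact.

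The documents make it plausible that withdrawal would differ by arm and relate to outcome:

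- **Burden.** Active NMES is 60 minutes a day, 5 days a week, at the strongest tolerated contraction, and Risks/Benefits expects some painful contractions and soreness. The sham emits no current.
- **Detection.** Real-time tracking is described for the NMES device. The sham is a different model, and no equivalent tracking is described for it.
- **Discretion.** The person who asks about compliance each week knows the allocation.
- **Link to outcome.** The Drug and Device section attributes disuse, and through it fiber atrophy and weakness, partly to pain. Pain could drive both non-compliance and a poor result.

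If the NMES volunteers who were doing worst were the ones withdrawn, the remaining NMES group would look better than the group that was randomised.

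**Working it through.** **1. The plan's own numbers.** For 10 completers per group and 20% loss:

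- 10 / (1 − 0.20) = 12.5, so 13 per group.
- 10 × 1.20 = 12 per group, the stated figure.
- 24 falling to 20 is a loss of 4/24 = 16.7%. A true 20% loss leaves 24 × 0.80 = 19.2.

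The gap is one volunteer per group and is not the point here. What matters is that the plan expects about 4 of 24 to be lost, so 4 is used below.

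**2. Is this a power problem?** The stated powers cannot be recomputed, because no baseline means are given. They can be inverted with a two-sample t test on the leg difference (two-sided 5% assumed, since sidedness is not stated). At 10 per group, 87% power for MHC I CSA implies a standardised effect of 1.46, and 80% for Aim 2 torque implies 1.325. Holding those effects fixed:

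| Analysed (NMES/sham) | MHC I CSA | Aim 2 torque |
|---|---|---|
| 10/10 (plan) | 87% | 80% |
| 12/12 | 93% | 87% |
| 8/12 | 86% | 78% |

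Even a fully one-sided loss of 4 costs only one or two points of power against the plan. The issue is possible bias.

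**3. Size of the bias under assumed inputs.** Assumptions, none of them from the documents: the outcome is the leg difference in SD units; compliance has correlation ρ with outcome, the same in both arms; there are 12 per arm; and the least compliant k are withdrawn from each arm.

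Bias = ρ × [m(k active) − m(k sham)], where m(k) is the expected mean compliance score, in SD units, of those left after the lowest k of 12 are removed. The four lowest expected standard normal order statistics for n = 12 are −1.629, −1.116, −0.793 and −0.537. All twelve sum to zero, so:

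- m(0) = 0
- m(1) = 1.629/11 = 0.148
- m(3) = (1.629 + 1.116 + 0.793)/9 = 0.393
- m(4) = (1.629 + 1.116 + 0.793 + 0.537)/8 = 0.509

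A simulation of 40,000 trials with no true effect agrees with the formula and supplies the type I error:

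| Withdrawn (NMES/sham) | ρ = 0 | ρ = 0.3 | ρ = 0.5 |
|---|---|---|---|
| 2/2 | 0 | 0 | 0 |
| 3/1 | 0 | 0.245 × 0.3 = 0.07 SD | 0.245 × 0.5 = 0.12 SD |
| 4/0 | 0 | 0.509 × 0.3 = 0.15 SD; type I error 6.3% | 0.509 × 0.5 = 0.25 SD; type I error 8.8% |

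Both conditions are needed: an imbalance between arms and a link with outcome. The sign favours NMES when less compliant volunteers do worse and more are withdrawn from the NMES arm. It reverses if either of these reverses.

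**4. Is there a safeguard elsewhere?** The SAP lists compliance with rehabilitation and activity restrictions as a possible Aim 2 covariate. That is not NMES compliance, and a covariate cannot bring back a volunteer with no outcome. The reminders in the Interventions section do not cancel the withdrawal rule.

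**The case against.** The strongest reply is that nothing here shows bias. The rule is permissive and worded alike for both arms. Intensity is chosen by the patient below the pain threshold, and Risks/Benefits says painful contractions are quickly eased by turning it down. Controls get the same frequency of staff contact, and volunteers told they are receiving something imperceptible might also skip sessions. The monitoring system exists to improve compliance, and its described response is to prompt and offer contact. No compliance figures by arm are given. All of this stands, and it is why the point is a risk without a safeguard.

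Three stronger readings are tempting and are not supported.

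- A reader might infer that the rule does bias the comparison. The table above shows zero bias under balanced or outcome-unrelated withdrawal.
- A reader might infer that allowing for dropout from 12 to 10 per group reveals a completer analysis. It is ordinary sample-size planning, and the SAP specifies neither a completer nor a per-protocol analysis.
- A reader might put a percentage on the overstatement. For Aim 2 the planned difference is 30 − 5 = 25 points. If 2 of 12 NMES volunteers gained nothing and were dropped, 25 would be reported against 25 × 10/12 = 20.8 as randomised, an excess of 20%. That presumes removal from one arm only and zero benefit in those removed, concerns the 6-month outcome and not the biopsy, and contrasts two estimands. It is not an estimate for this trial.

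A last objection also stands: a volunteer who will not return has no outcome whether formally withdrawn or not. Changing the rule recovers only those willing to attend.

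**Conclusion.** The concern holds as a risk. The protocol lets staff end the participation of randomised volunteers for non-compliance or missed visits, the primary outcome is lost if that happens before the 3-week biopsy, and neither document keeps such volunteers in follow-up or states an as-randomised analysis. Whether bias results depends on withdrawals differing by arm and relating to outcome. The documents make that plausible but do not establish it.

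With 4 of 24 withdrawn, the illustrative size runs from zero to about 0.25 SD, with type I error up to 8.8% in the most one-sided case. The splits and correlations (0.3 to 0.5) are assumptions. Against implied planned effects of about 1.3 SD or more, the bias is modest. It is still worth removing in a study of 12 per arm that added a sham specifically to reduce bias and is meant to inform a later trial.

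**What to change.** Amend Withdrawal Procedures so that non-compliance with the device, or a missed visit, is not by itself a ground for withdrawal from the study. State that such volunteers, if they consent, are still invited to the planned 3-week biopsy and 6-month tests. Leave safety-based withdrawal as it is.

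In the SAP, state that all volunteers with outcome data are analysed in the arm to which they were randomised. Report adherence and withdrawals by arm and reason, add a missing-data sensitivity analysis, and keep any per-protocol result supportive. The same accounting should show separately any sham volunteers who decline use of their data at debriefing, since that loss can occur in one arm only.

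The cost is wording in two documents, because the visits are already planned. The downsides are that the estimated effect may be somewhat diluted by non-adherent volunteers, and that those who do not return will still lack outcomes. If all 12 per arm were measured and the planned effects held, power would rise from 87% to about 93% for MHC I CSA and from 80% to about 87% for torque, which offsets part of the dilution.

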***Sources of Materials:***

An individual research record will be kept on each volunteer in compliance with HIPAA standards. This record will contain identifying data, demographic information and results from all clinical research measurements and evaluations. The results of all testing will be kept confidential. In addition, skeletal muscle tissue samples will be taken and will be used for measurement of muscle size, structure and function. All materials gathered in conjunction with the proposed studies will be used for research purposes only and will be available only to research personnel working on these studies, who have obtained proper training in human subjects research and privacy protection.

**DRUG AND DEVICE INFORMATION**

**Drug (s)**  *Not applicable*

**Device (s)**  *Not applicable*

The interventional device used in this study: EMPI Continuum complete electrotherapy system has received FDA approval (501K: K093324) for retarding disuse-related atrophy, which we believe is one of the primary mechanisms whereby muscle adaptations evolve in patients in the early, post-surgical period. That is, muscle disuse secondary to pain, limited range of motion and muscle weakness (the latter being due to neural inhibition caused by joint pain/swelling) causes skeletal muscle fiber atrophy and weakness.

For the control intervention, an EMPI 300PV that is modified to have its leads disconnected within the device will be used. For both leads on the device (1 and 2), the ferrites directly proximal to the leads are removed and a dummy load resistor (1 Megohm) is used to bridge the output to simulate the resistance of human skin (see Appendix 3). This bridging is necessary, as the device will not function if no load is detected. This yields a device that cannot deliver any electrical stimulus to the patient throughout the stimulus intensity range of the device.

*FDA approval:*

The EMPI Continuum is approved to mitigate muscle atrophy/dysfunction associated with muscle disuse (501K: K093324).

*Risk assessment:*

The device (and similar devices) has been used extensively in the orthopedic and neural rehabilitation settings by physical and occupational therapists and in numerous disease states (heart failure, chronic obstructive pulmonary disease, knee replacement) to improve muscle size and function in clinical trial settings. Thus, NMES is generally a safe modality, with a long safety record. Although evidence is limited, some have suggested that NMES could increase the risk of dislodging a deep vein thrombosis (DVT) because of the rhythmic muscle contractions induced by the electrical stimulation. However, several published reports show that NMES significantly reduces the risk of developing DVTs. In fact, the device we are using is FDA-approved for prevention of DVT of the calf muscles immediately following surgery, as it would function similar to intermittent pneumatic compression. Moreover, the population we are studying is generally at low risk for DVT and we will actively exclude any individual with a known coagulopathy or DVT. Because of the location of the stimulating electrodes (upper leg), the risk of NMES dislodging a DVT is likely minimal. Finally, during the first couple of NMES sessions, muscle soreness may occur, but this is comparable to what might occur with classical exercise training and dissipates over time.

## **SUBJECT CHARACTERISTICS, IDENTIFICATION AND RECRUITMENT**

*Subject Selection:*

A single cohort of patients will provide data to address both aims. Patients with recent, unilateral ACL rupture or combined ACL rupture/meniscus injury, who are undergoing surgical reconstruction, will be recruited and randomized to NMES or control, with stratification for age, sex and graft type (knee extensor autograft, knee flexor autograft and allograft). A within-subject design will be used (Fig 3), where the injured, surgically-treated leg will be compared to the contralateral, uninjured leg.

We chose to study patients with ACL rupture, with or without meniscus injury, as this trauma is immediately disabling, dramatically reduces muscle strength and increases the risk of further injury and developing PTOA (1-4). Although neuromuscular adaptations differ slightly between ACL and combined ACL/meniscus injury post-surgery, injury types will be distributed equally by randomization. Inclusion of both injury types provides broader generalizability of our results. We will also stratify randomization by graft type (knee extensor autograft, hamstring autograft and allograft groups) using an adaptive randomization approach to assure that groups are frequency matched for the different graft types.

Use of the uninjured leg as a within-subject control is common in this field and justified by results from our labs (4) and others (5) showing that its size and function are maintained throughout the proposed study period (4, 5). While whole muscle strength in the uninjured leg is reduced slightly compared to uninjured control volunteers due to cross-over neural inhibition (6), there is no evidence that this would affect the intrinsic structure or function of its single muscle fibers differently in NMES and control groups. Nonetheless, we will assess strength in the uninjured leg repeatedly throughout the study to verify its constancy and, in turn, its suitability as a within-subject control, particularly for the secondary aim.

